11.1.2 Other significant adverse events

During the evaluation of the AE data, an AstraZeneca medically qualified expert will review the list of AEs that were not reported as SAEs and discontinuation of IP due to AEs. Based on the expert's judgement, significant AEs of particular clinical importance may, after consultation with the Global Patient Safety Physician, be considered other significant AEs (OAEs) and reported as such in the CSR. A similar review of laboratory/vital signs/ECG data will be performed for identification of OAEs.

Examples of these are marked haematological and other laboratory abnormalities, and certain events that lead to intervention (other than those already classified as serious), dose reduction or significant additional treatment.

11.2 Calculation or derivation of patient reported outcome variables

Scoring of the HRQoL SF-36 will be conducted as per the SF-36 Health Survey Manual and Interpretation Guide ([Ware et al 2007](#)). The 8 domains plus 2 overall summary scores, (the physical component score and the mental health component score), will be derived at the end-of-treatment (Day 28) visit.

If less than 50% of the items in 1 scale are missing, the mean scores for the completed items will be used for imputation. If 50% or more of the items in 1 scale are missing, that subscale will be treated as missing. The SF-36 (including the 8 subscores and the physical component

score and mental component score) will be summarised in terms of change from baseline. Change from baseline in the scores will be calculated at the end-of-treatment (Day 28) visit.

The symptoms site questionnaire will be calculated as change from baseline at each scheduled assessment post-baseline (Day -1). The symptoms diary questionnaire will be calculated as change from baseline as the mean of daily assessments for Day 1 to Day 7, Day 8 to Day 14, Day 15 to Day 21, and Day 22 to Day 28, respectively.

11.3 Calculation or derivation of pharmacokinetic variables

The PK analyses will be the responsibility of pharmacokineticist at . standard operating procedures (SOPs) and Work Instructions will be used as the default methodology, if not otherwise specified. The actual sampling times will be used in the PK calculations.

Pharmacokinetic parameters will be derived using standard noncompartmental methods with WinNonlin[®] Professional Version 5.2, or higher (Pharsight Corp., Mountain View, California, United States). All PK computations will be performed using WinNonlin[®] Professional Version 5.2 (or higher), or SAS[®] Version 9.2 or higher (SAS Institute, Inc., Cary, North Carolina, United States).

Patients who withdraw from the study following administration of the IP, but prior to study completion, will be included in the PK analysis provided they have evaluable concentrations over the planned collection period. Patients with partial data will be evaluated on a case-by-case basis to determine if sufficient data are available for meaningful analysis.

Where possible, the following PK parameters will be determined for AZD4901 and AZ12592232 for Day 7 and Day 28:

- C_{\max} : Maximum observed plasma concentration.
- t_{\max} : time of C_{\max} .
- $AUC_{(0-8)}$: Area under the plasma concentration-time curve from time zero to 8 hours calculated by linear up/log down trapezoidal summation.
- C_{\min} : predose concentration
- C_{\max} metabolite to parent ratio: The ratio of AZ12592232 C_{\max} to AZD4901 C_{\max}
- $AUC_{(0-8)}$ metabolite to parent ratio: The ratio of AZ12592232 $AUC_{(0-8)}$ to AZD4901 $AUC_{(0-8)}$

The following will be calculated for 4- β -OH cholesterol and 6- β -OH testosterone:

- Ratio of post treatment:pre treatment concentration

11.4 Calculation or derivation of pharmacodynamic variable(s)

The PD analyses will be performed at _____ with select analyses performed by AstraZeneca or designee. _____ SOPs and Work Instructions will be used for analyses performed by _____ as the default methodology if not otherwise specified.

Change-from-baseline (Day-1) for LH, FSH, free and total testosterone concentrations, and the components of the monitoring sample (estradiol [E2], progesterone, prolactin, TSH, T4 [total and free], HbA_{1c}, and IGF-1), as appropriate, will be calculated as:

- Absolute change: $X_t - X_0$
- Percent change from baseline: $100 \times (X_t - X_0) / X_0$
- Ln-ratio: $\ln(X_t / X_0)$

where X_t is a patient's measured value at time t and X_0 is the time matched measurement at baseline for LH, FSH and free and total testosterone and a single value baseline for other analytes listed above.

Primary

- LH AUC₍₀₋₈₎ on Day 7: Area under the plasma concentration-time curve from time zero to 8 hours calculated by linear up/log down trapezoidal summation on observed concentrations

Secondary

- Change-from-baseline (Day-1) for free and total testosterone concentrations on Days 7 and 28
- AUC₍₀₋₈₎ for LH on Day 28 on observed concentrations

Where possible, the following PD parameters will be determined for observed concentrations of LH, testosterone, and FSH samples collected on Days -1, 7, and 28:

- AUC₍₀₋₈₎ for LH
- Free and total testosterone AUC₍₀₋₈₎, calculated by linear up/log down trapezoidal summation
- FSH AUC₍₀₋₈₎, calculated by linear up/log down trapezoidal summation
- An evaluation of LH pulse interval and amplitude ([Johnson 2008](#)) (to be performed by AstraZeneca)

- Free and total testosterone C_{\max} : Maximum observed plasma concentration, obtained directly from the observed concentration versus time data
- Free and total testosterone C_{\min} : Minimum observed plasma concentration, obtained directly from the observed concentration versus time data
- FSH C_{\max} , obtained directly from the observed concentration versus time data.
- FSH C_{\min} , obtained directly from the observed concentration versus time data.

12. STATISTICAL METHODS AND SAMPLE SIZE DETERMINATION

12.1 Description of analysis sets

12.1.1 General principles

The analysis of data will be based on different subsets according to the purpose of analysis, ie, for PD, safety, and PK, respectively.

The as-treated principle will be applied to all evaluations; ie, patients who received another treatment than the one assigned in the randomization list will be analysed as belonging to the actual treatment group and not that assigned by randomisation.

In general, descriptive statistics will follow the rounding convention in SOPs.

12.1.2 Safety analysis set

All patients who receive at least 1 dose of IP, including placebo, and for whom any postdose data are available will be included in the safety population.

12.1.3 Pharmacokinetic analysis set

The PK analysis set will be a subset of the safety analysis set and will include only patients who receive at least 1 dose of AZD4901 and have at least 1 postdose PK measurement without important CSP deviations or violations thought to significantly affect the PK (eg, patient vomited at or before 2 times median t_{\max} , wrong dose administered, prohibited concomitant medication, etc).

For the evaluation of the 4- β -OH cholesterol and 6- β -OH testosterone results, this population will be further restricted to include only patients who did not receive any inhibitors/inducers within 12 weeks prior to dosing.

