6.5.2 Determination of drug concentration

Samples for the determination of concentrations of AZD4901 and its metabolite, AZ12592232, in plasma _____ on behalf of Clinical Bioanalysis Alliance, AstraZeneca R&D, using an appropriate bioanalytical method. Full details of the analytical methods used will be described in a separate bioanalytical report.

All samples still within the known stability of AZD4901 and AZ12592232 at time of receipt by the bioanalytical laboratory will be analysed.

For each placebo patient, samples will only be analyzed on a 'for cause' basis, eg, if no quantifiable concentrations were observed in a patient's samples when the drug was expected to be present.

Additional analyses may be conducted on the biological samples to further investigate the presence and/or identity of drug metabolites. Any results from such analyses, if performed, will be reported separately from the CSR.

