7. BIOLOGICAL SAMPLING PROCEDURES

7.1 Volume of blood

The total volume of blood that will be drawn from each patient in this study is presented in Table 5.

Table 5 Volume of blood to be drawn from each subject

Assessment		Sample volume (mL)	No. of samples	Total volume (mL)
Safety	Clinical chemistry	2.0	8	16.0
	Haematology/HbA _{1c} ^a	1.2	8 ^b	9.6
	Serology	2.0	1	2.0
	Serum pregnancy	1.1	1	1.1
PD	LH/FSH	1.1	150 ^c	165.0
	Testosterone (total)	2.0	30	60.0
	Testosterone (free)	2.0	30	60.0
	TSH/T4 (total and free) ^a	1.1	5	5.5
	Estradiol ^a	1.1	4	4.4
	Progesterone, prolactin ^{a,d}	1.1	5	5.5
	IGF-1 ^a	1.1	4	4.4
	AZD4901/AZ12592232	1.2	20	24.0
PK	4-β-OH cholesterol	3.0	2	6.0
	6-β-OH testosterone	2.0	2	4.0
Pharmacogenetic		6.0	1	6.0
Discard volume ^e				147
Total				520.5

^a Component of monitoring sample (estradiol, progesterone, prolactin, TSH, T4 (total and free), HbA_{1c}, and IGF-1).

^b Includes HbA_{1c} (component of the monitoring sample) on Days -1, 28, and follow-up.

^c Includes FSH at screening (single sample) and on Days -1, 7, and 28 (9 samples on each day), and at follow-up (single sample).

^d A single sample of prolactin only will be collected at screening to confirm eligibility.

- ^e If using an indwelling catheter, 1.0 mL of blood will be removed to flush the catheter prior to each serial PD sample collection time point.

The maximum volume to be drawn from each patient will not exceed 530 mL.

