12.1.4 Pharmacodynamic analysis set

The PD analysis set will include all patients who receive at least 1 dose of AZD4901 or placebo and for whom evaluable PD data appropriate for the evaluation of interest are

available without important CSP deviations or violations thought to significantly affect either the PK or PD.

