12.2.5 Pharmacokinetics

The PK blood sample collection times, as well as derived sampling time deviations, and plasma concentrations will be listed for all patients. Plasma concentrations will be summarised by treatment using descriptive statistics (eg, n, arithmetic mean, SD, minimum, median, maximum, geometric mean, and CV).

Plasma concentrations that are below the lower limit of quantitation (LLOQ) will be handled as follows:

- At a time point where less than or equal to 50% of the values are below the limit of quantitation (BLQ), all BLQ values will be set to LLOQ, and all descriptive statistics will be calculated.
- At a time point where more than half of the values are BLQ, the mean, SD, geometric mean and CV will be set to Not Determined. The maximum value will

be reported from the individual data, and the minimum and median will be set to BLQ.

- If all values are BLQ at a time point, no descriptive statistics will be calculated for that time point. Not applicable will be reported for SD and CV and BLQ will be reported for mean, geometric mean, minimum, median, and maximum.
- The number of BLQ values (n below LLOQ) will be reported for each time point.

Plasma parameters will be summarised by treatment using descriptive statistics (eg, n, arithmetic mean, SD, minimum, median, maximum, geometric mean, and CV). For t_{\max} , only n, median, minimum, and maximum will be reported.

Data from patients excluded from the PK analysis set will be included in the data listings, but not in the summaries.

Concentration and PK parameters [$AUC_{(0-8)}$, C_{\min} , and C_{\max}] for AZD4901 and AZ12592232 will be presented graphically for Day 7 and Day 28 for each treatment.

Results for 4- β -OH cholesterol and 6- β -OH testosterone will be summarised by treatment and collection time. For 4- β -OH cholesterol and 6- β -OH testosterone, descriptive statistics will include the ratio of post treatment to pre treatment concentration with 90% confidence intervals (CIs) calculated by ln-transformed data.

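### The two CYP3A4 markers are summarised only in AZD4901-treated patients, so a change common to all arms stays in the Day 28/Day -1 ratio although placebo patients give the same samples

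*Protocol*

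**What the plan says.** Section 12.1.3 defines the PK analysis set as one that "will include only patients who receive at least 1 dose of AZD4901 and have at least 1 postdose PK measurement". For the two CYP3A4 markers it adds that "this population will be further restricted to include only patients who did not receive any inhibitors/inducers within 12 weeks prior to dosing". The marker set is thus a subset of a set limited to patients who took AZD4901.

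Section 12.2.5 says of the markers that results "will be summarised by treatment and collection time" and that "descriptive statistics will include the ratio of post treatment to pre treatment concentration with 90% confidence intervals (CIs) calculated by ln-transformed data". It specifies no comparison with placebo. Earlier in the same section: "Data from patients excluded from the PK analysis set will be included in the data listings, but not in the summaries".

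The samples themselves are not limited to active arms. Section 6.5.1 and Tables 1 and 2 schedule both markers on Day -1 and Day 28 without a treatment exception. Section 7.1 states that "The total volume of blood that will be drawn from each patient in this study is presented in Table 5", and Table 5 counts two samples of each marker.

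Section 3.2 gives the reason for measuring them: 4-beta-OH cholesterol as an early sign of whether AZD4901 may induce CYP3A4, and 6-beta-OH testosterone to help show that a testosterone fall comes from NK3R action and not from altered CYP3A4 metabolism.

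**The concern.** Both purposes in Section 3.2 are causal: is the change due to AZD4901? A within-arm Day 28/Day -1 ratio answers that only if nothing else moves the marker over about four weeks. The trial randomises a placebo arm and draws its marker samples, but the analysis set leaves that arm out of the summaries.

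The mismatch is sharpest for testosterone. Section 12.2.6 analyses testosterone AUC, Cmax and Cmin as baseline-adjusted ratios versus placebo. The marker meant to help explain that controlled result is reported without a control, so the two estimates are not on the same footing. A shared change could look like induction or inhibition, or could offset a real effect.

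**Working it through.** **Does any text bring placebo back?**

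| Place in the protocol | Content | Placebo in the marker summaries? |
|---|---|---|
| 12.1.3, PK set | At least one dose of AZD4901 required | No |
| 12.1.3, marker set | The PK set narrowed further | No |
| 12.2.5, patients outside the PK set | Listed, not summarised | No |
| 12.2.5, marker paragraph | Summarised by treatment | Silent; does not override 12.1.3 |
| 6.5.2, for-cause assay rule | AZD4901 and its metabolite | Does not apply to the markers |
| 6.5.3, marker assays | No limit by treatment | Placebo results can be available |

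The contrast with Section 12.1.4 is informative: "The PD analysis set will include all patients who receive at least 1 dose of AZD4901 or placebo". There placebo is named; in the PK set it is not. A patient on placebo throughout cannot enter the marker set, so none of the 14 planned placebo patients would be summarised.

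**Size, as an illustration.** There is no plan figure to reproduce: the protocol states no marker SD, drift or decision rule.

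Inputs:
- n = 12 evaluable patients per arm (Section 12.3).
- 90% CI on the ln scale (Section 12.2.5).
- Assumed SD of ln(Day 28/Day -1): 0.15, 0.25 and 0.35.
- Assumed common drift: 10% and 15%, with no drug effect.

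The within-arm interval is mean ± t(0.95; 11) × SD/√12, with t = 1.796. The chance that it excludes 1 follows from a noncentral t with 11 df and noncentrality ln(1 + drift)/(SD/√12). For 15% drift and SD 0.25, this is 0.1398/(0.25/3.464) = 1.94, which gives 0.57.

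| Common drift | SD 0.15 | SD 0.25 | SD 0.35 |
|---|---|---|---|
| none | 10% | 10% | 10% |
| 10% | 66% | 34% | 23% |
| 15% | 92% | 57% | 37% |

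In a ratio versus placebo, a drift common to both arms cancels on the ln scale, so the figure stays at 10% in every cell.

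**Price in precision.** With the pooled SD from a four-arm model with treatment only (48 − 4 = 44 residual df, t = 1.680), the versus-placebo half-width is 1.680 × SD × √(2/12) = 0.686 SD. Within an arm it is 1.796 × SD/√12 = 0.518 SD. The ratio is 0.686/0.518 = 1.32. Adding the ln-baseline covariate costs one df and leaves this at 1.32, apart from any effect of the covariate on the residual SD.

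**The case against.** Several points on the other side are sound.

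- **Role of the markers.** They appear in none of the objectives in Sections 2.1 to 2.3, Section 3.2 words their purpose cautiously, and Section 12.2.5 calls the output descriptive. This stands and limits the severity.
- **No decision rule.** The protocol nowhere says that a 90% CI excluding 1 means induction. The percentages above describe how an uncontrolled interval behaves. They are not the error rate of a planned test.
- **Assumed drift.** Drift may be small. Section 5.1 bars grapefruit and Seville oranges, Section 5.6 restricts CYP3A4 and CYP2C9 inhibitors and inducers, and hormonal contraception must stop 8 weeks before dosing. These rules reduce some sources of a common change but do not remove all of them. With no drift the within-arm interval behaves nominally.
- **Partial separation.** A common drift would be equal across the three regimens, so a dose trend would point to the drug. Placebo values also remain in the listings. However, a dose trend estimates neither the drift nor the absolute effect, and listings give no estimate.
- **Possible drafting slip.** The sentence on exclusion from summaries follows the drug concentration rules and precedes the marker paragraph, and a summary by treatment might be meant to include placebo. Section 12.1.3 still points the other way, and nothing resolves it in favour of placebo.

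A reader might also infer that placebo marker samples are never assayed, because "For each placebo patient, samples will only be analyzed on a 'for cause' basis". That rule sits in Section 6.5.2, which covers the drug and its metabolite. Section 6.5.3, on the markers, has no such limit.

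**Conclusion.** The concern holds as a should-fix. As written, the marker summaries exclude the concurrent randomised control, and a change common to all arms is not removed from the estimates used for the causal purposes in Section 3.2.

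The size cannot be taken from the protocol. Under the stated assumptions (n = 12, no drug effect, 10% to 15% common drift, SD 0.15 to 0.35), a within-arm 90% CI excludes 1 in about 23% to 92% of cases, against 10% for a ratio versus placebo.

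Two stronger readings are not supported. A reader might infer that a drug effect cannot be separated from drift at all; the three regimens and the listed placebo values allow partial separation. A reader might also infer that the trial's main conclusions are at risk; the primary LH analysis and the secondary PD analyses use the PD set, which includes placebo, and report ratios versus placebo. The consequence is confined to the two markers and to the support they lend to interpreting testosterone.

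**What to change.** - **Section 12.1.3:** define a separate marker set of all dosed patients, placebo included, who have Day -1 and Day 28 marker values, with the existing inhibitor/inducer restriction.
- **Section 12.2.5:** summarise placebo alongside the active arms and report the Day 28/Day -1 ratio versus placebo with a 90% CI, calculated on the ln scale. The Section 12.2.6 model (treatment, with ln-baseline as covariate) can be used as it stands. Keep the within-arm ratios as descriptive output.

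Make the change before unblinding, so that adding the control is not a post-hoc choice. The cost is wording in two sections and one extra model per marker, with no new samples or visits. The versus-placebo CI is about 1.3 times as wide on the ln scale as the within-arm CI.

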12.1.4 Pharmacodynamic analysis set

The PD analysis set will include all patients who receive at least 1 dose of AZD4901 or placebo and for whom evaluable PD data appropriate for the evaluation of interest are

available without important CSP deviations or violations thought to significantly affect either the PK or PD.

12.2 Methods of statistical analyses

12.2.1 General principles

The PD (except the evaluation of LH pulse interval and amplitude), PK, and safety summaries, individual figures, and data listings, as well as the statistical analysis of PK variables will be the responsibility of the study biostatistician at using SAS[®] Version 9.2 or higher and, where appropriate, additional validated software. An evaluation of LH pulse interval and amplitude will be performed by AstraZeneca or designee.

Quantitative continuous variables will be summarised using descriptive statistics, including n, mean, standard deviation (SD), median, minimum, and maximum values. Additionally, for PK parameters, (except for t_{max}), geometric means and geometric coefficient of variation (CV) will be reported. The geometric mean is calculated as the exponential of the arithmetic mean calculated from data on a ln scale. The CV is calculated as $100 \cdot \sqrt{(\exp(s^2) - 1)}$ where s is the SD of the data on a ln scale. Mean, SD, geometric mean, and CV will not be calculated for t_{max} .

Categorical variables (eg, gender) will be summarised in frequency tables (frequency and proportion of patients in the analysis set).

In general, descriptive statistics will follow the rounding convention in

Baseline characteristics will be summarised across all patients.

12.2.2 Subject characteristics

Continuous variables will be summarised using descriptive statistics (n, mean, SD, minimum, median, and maximum) and categorical variables will be summarised in frequency tables (frequency and proportion) for each treatment and for all patients overall.

12.2.3 Safety

All safety data (scheduled and unscheduled) will be presented in the data listings.

Safety variables (eg, clinical laboratory values and vital signs) will be reported to the same precision as the source data. Derived variables will be reported using similar precision to those from which they were derived.

Extra measurements (such as unscheduled or repeat assessments) will not be included in the descriptive statistics by scheduled time point, but will be included in data listings. All AEs and clinical laboratory outliers that occur following the first dose of IP will be included in the

tabulations of AEs and outlier events, including episodes that occur at unscheduled evaluations.

All available data from patients in the safety analysis set will be included in the safety analyses. No adjustment or imputation will be utilised for missing values or for patients who withdraw prior to completing the study, neither will analyses be restricted to patients with complete data.

Adverse events beginning at the time of first IP administration will be summarised by preferred term and system organ class using MedDRA vocabulary by treatment and across all AZD4901 treatments. Furthermore, listings of SAEs and AEs that lead to withdrawal will be made and the number of patients who have any AEs, SAEs, AEs that lead to withdrawal, and AEs with severe intensity will be summarised.

Tabulations and listings of data for vital signs and clinical laboratory tests will be presented, as appropriate. Electrocardiogram results, physical examination findings, and C-SSRS assessments will be listed. All continuous safety data will be summarised across all treatments for the observed value at each scheduled assessment and for the corresponding change from baseline. For clinical laboratory tests, listings of values for each patient will be presented with abnormal or out-of-range values flagged. Clinical laboratory data will be reported in Système International units in the CSR.

